### 7.1.3. Methods

Descriptive summary table will be provided for overall study population, and by each arm, respectively. The summary statistics for continuous variables will include sample size, mean, standard deviation (SD), median, minimum and maximum for both baseline and post-baseline measurements (if applicable). The summary statistics for categorical variables will include sample size, frequency and percentages. The difference between the two arms will be examined if applicable. Fisher's exact test will be proposed to test the difference between two arms for categorical variables.

## 7.2. Sample Size and Power

This feasibility study is to assess the ability to enroll and randomize patients with chronic GVHD to discontinuation versus continuation of IST. Sample size of 40 patients is based on the anticipated availability of eligible patients. Although the study is not powered based on a specific null hypothesis, if 20 patients are enrolled in each arm, we will have 83% power to see statistically significant difference between two arms (at the two-sided level of 0.1) if the true 12 months rate of IST resumption in discontinuation IST arm is 75% and true 12 months rate of increase IST dose in investigation arm is 30%.

## 8. Risks and Discomforts

Prolonged IST on the continuation IST arm (investigational arm) may result in increased risk of infection, treatment related organ toxicity, and increased risk for relapse. Earlier discontinuation of IST on the discontinuation arm (standard of care) may result in increased risk for GVHD exacerbation, required initiation of high dose immunosuppression, which again may result in increased risk of infection, treatment

related organ toxicity, and increased risk for relapse. Treatment of any complication will be at the discretion of the patient's provider.

Blood collection for research purposes will usually be done at the same time as clinical sampling.

## **9. Potential Benefits**

Based on retrospective data demonstrating that approximately 50% of patients who stop IST require resumption of IST due to GVHD exacerbation, the continuation arm of this study (investigational arm) offers potential benefit of decreasing the risk of chronic GVHD exacerbation and decreasing the need for resuming high-dose IST.

## **10. Adverse Events/Serious Adverse Events**

### **10.1 Adverse Events**

According to ICH guidelines (Federal Register. 1997; 62(90):25691-25709) and 21 CFR 312.32, IND Safety Reports, and ICH E2A, Definitions and Standards for Expedited Reporting, an adverse event is defined as follows:

*An adverse event is any untoward medical occurrence in a clinical investigation subject administered a medicinal product and which does not necessarily have a causal relationship with this treatment. An AE can therefore be any unfavorable and unintended sign (including an abnormal laboratory finding), symptom, or disease temporally associated with the use of a medicinal product, whether or not considered related to the medicinal product.*

*Abnormal laboratory values for laboratory parameters specified in the study should not be recorded as an adverse event unless an intervention is required (repeat testing to confirm the abnormality is not considered intervention), the laboratory abnormality results in a serious adverse event or the adverse event results in study termination or interruption/discontinuation of study treatment.*

*Medical conditions present at screening (i.e., before the study treatment is administered) are not adverse events and should not be recorded on adverse event pages of the CRFs. These medical conditions should be adequately documented on the subject chart. However, medical conditions present at baseline that worsen in intensity or frequency during the treatment or post-treatment periods should be reported and recorded as adverse events.*

Events that do not meet the definition of an AE or SAE include:

- Any clinically significant abnormal laboratory finding or other abnormal safety assessments that is associated with the underlying disease, unless

- judged by the investigator to be more severe than expected for the subject's condition.
- The disease/disorder being studied, or expected progression, signs, or symptoms of the disease/disorder being studied, unless more severe than expected for the subject's condition
  - Medical or surgical procedure (e.g., endoscopy, appendectomy); the condition that leads to the procedure is an AE
  - Situations where an untoward medical occurrence did not occur (social and/or convenience admission to a hospital)
  - Anticipated day-to-day fluctuations of pre-existing disease(s) or condition(s) present or detected at the start of the study that do not worsen
  - Clinical events or laboratory findings related to immunosuppressive therapy

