## 6.6 Adverse Reactions and their Management

Prolonged IST on the continuation IST arm may result in increased risk of infection, treatment related organ toxicity, and increased risk for relapse. Earlier discontinuation of IST on the discontinuation arm may result in increased risk for GVHD exacerbation, required initiation of high dose immunosuppression, which again may result in increased risk of infection, treatment related organ toxicity, and increased risk for relapse. Treatment of any complication will be at the discretion of the patient's provider.

Blood collection for research purposes will usually be done at the same time as clinical sampling.

If an adverse event occurs as a result of study participation, the PI will ensure appropriate follow-up is carried out until the effects of the adverse event are resolved. If the study staff becomes aware of any unanticipated severe adverse reactions due to study participation, the circumstances will be reported to the IRB. To note, clinical events and/or laboratory findings related to IST will not be reported as adverse events, since both discontinuation or prolonged continuation of IST are used in practice.

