## 10.2 Serious Adverse Events

An adverse event should be classified as an SAE if it meets one of the following criteria:

Fatal	Adverse event results in death.
Life threatening:	The adverse events placed the subject at immediate risk of death. This classification did not apply to an adverse event that hypothetically might cause death if it were more severe.
Hospitalization:	It required or prolonged inpatient hospitalization. Hospitalizations for elective medical or surgical procedures or treatments planned before enrollment in the treatment plan or routine check-ups are not SAEs by this criterion. Admission to a palliative unit or hospice care facility is not considered to be a hospitalization.
Disabling/incapacitating	Resulted in a substantial and permanent disruption of the subject's ability to carry out normal life functions.
Congenital anomaly or birth defect:	An adverse outcome in a child or fetus of a subject exposed to the molecule or treatment plan regimen before conception or during pregnancy.
Medically significant:	The adverse event did not meet any of the above criteria, but could have jeopardized the subject and might have required medical or surgical intervention to prevent one of the outcomes listed above.

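### Serious events attributed to immunosuppression have no stated route to the DSMC, although prolonged immunosuppression is the strategy under test

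*Combined protocol and SAP*

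**What the plan says.** Section 10.1 opens its list of exclusions with "Events that do not meet the definition of an AE or SAE include" and closes it with "Clinical events or laboratory findings related to immunosuppressive therapy". Section 6.6 says that "clinical events and/or laboratory findings related to IST will not be reported as adverse events". Section 10.5 repeats this for clinical events but does not mention laboratory findings. Sections 6.6 and 10.5 give the same reason: both strategies already occur in routine care.

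Other provisions bear on the point:

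- **AE definition (10.1).** It applies "whether or not considered related to the medicinal product".
- **Laboratory rule (10.1).** An abnormal value counts as an AE if it requires intervention, or if "the laboratory abnormality results in a serious adverse event or the adverse event results in study termination or interruption/discontinuation of study treatment".
- **SAE definition (10.2).** "An adverse event should be classified as an SAE if it meets one of the following criteria".
- **Reporting (10.5).** AEs and SAEs go to the DSMC at least once a year. Unanticipated severe reactions due to participation go to the IRB.
- **Named risks (6.6, repeated in section 8).** "Prolonged IST on the continuation IST arm may result in increased risk of infection, treatment related organ toxicity, and increased risk for relapse". Section 1 adds secondary malignancy as a risk of IST.
- **Status of the arms (1, 6.1).** Continuation is the investigational arm and discontinuation is standard care.
- **Endpoints (3.2, 7.1.2).** Relapse by 12 months, grade 3 or higher infection and grade 3 or higher organ toxicity are secondary endpoints, summarized descriptively and by arm.

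**The concern.** The trial randomizes patients to longer or shorter immunosuppression, and the exclusion removes events attributed to immunosuppression from safety reporting. Read literally, a fatal infection that the investigator ascribes to the continued drug is not an AE and so not an SAE. It is then outside the only material the protocol says the DSMC receives. The reason given may justify not reporting expected minor drug effects. It does not explain leaving out deaths and hospitalizations when one arm is called investigational.

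A second problem follows. Whether an event counts as an AE depends on a causality judgement, and section 6.5 has the clinician told the assigned arm. By-arm AE counts would then depend partly on open-label attribution. The exclusion can operate in both arms, because section 6.6 expects flares after discontinuation to bring high-dose IST with its own infections and toxicity. The direction and size of any distortion are therefore unknown.

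**Working it through.** The plan gives no figure on this point, so the check sets the provisions side by side.

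**Step 1. Is the exclusion limited?** The list in section 10.1 has six items:

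| Item | Limit |
|---|---|
| Laboratory or other safety finding associated with the underlying disease | Kept as an event if more severe than expected |
| The disease under study or its expected course | Kept "unless more severe than expected for the subject's condition" |
| Medical or surgical procedure | The condition behind it remains an AE |
| No untoward occurrence (e.g. social admission) | Nothing to report |
| Day-to-day fluctuation of existing disease | Only if it does not worsen |
| IST-related clinical event or laboratory finding | None |

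Two items carry a severity limit and three others are bounded by their nature (2 + 3 = 5). The IST item is the one remaining item of six that removes an untoward event without any limit.

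**Step 2. Can a serious event return through section 10.2?** There are six criteria: fatal, life-threatening, hospitalization, disabling, congenital anomaly and medically significant. The lead-in makes all six conditional on the event already being an adverse event, so 0 of 6 brings an IST-attributed event back.

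**Step 3. Does another route reach the DSMC?**

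- *Section 10.5, IRB reporting:* goes to the IRB, and only for unanticipated reactions. Infection and organ toxicity are anticipated in section 6.6.
- *Section 10.3:* makes some progression of the disease under study an SAE. It does not cover infection or organ toxicity from IST.
- *Sections 3.2 and 7.1.2:* three risks are collected as endpoints, but no DSMC reporting is stated for them.
- *Section 6.4:* survival is determined at annual chart review after active follow-up, again with no stated DSMC report.
- *Section 11:* the review committees look at accrual, adverse events, stopping rules and adherence to the monitoring plan. Endpoints are not named. The only stopping rule, in section 4, concerns accrual.

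None of these states a DSMC route for a serious infection or organ toxicity attributed to IST.

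**Step 4. Which named risks are collected elsewhere?** Sections 1 and 6.6 together name four: infection, organ toxicity, recurrent malignancy and secondary malignancy. Section 3.2 lists three as endpoints, two of them only at grade 3 or higher. Secondary malignancy is not listed (4 − 3 = 1).

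**Step 5. Is section 10 consistent with itself?** The AE definition disregards relatedness, yet the IST item makes relatedness decisive. Section 10.5 asks for relatedness to study drug, and section 10.7 counts definite, probable and possible as related to the study agent. For IST, an event so rated has already been excluded. If the 10.7 rule also governs the word related in 10.1, which the text does not say, even a possible link to IST would remove an event.

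**The case against.** The strongest reply is that this is a deliberate and disclosed choice. It appears three times, twice with its reason, in patients who were already taking an IST agent. The main harms are collected as endpoints without any attribution condition, with provider assessments every three months and monthly contact. The trial's own safety comparison therefore does not rest on AE classification. Section 11 also places the study under an institutional monitoring plan, with DSMC review at least annually and as needed, and that plan may send the DSMC more than the protocol states.

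Much of this stands as a limit on the claim. The harms in section 3.2 are not lost, and the institutional plan is not in the documents. What can be shown is that no route is stated, not that the DSMC would fail to see the events. But an endpoint summary by arm is not a stated report to the DSMC, and disclosing a reason does not make it adequate for serious events.

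It can also be argued that sections 10.5 and 10.7 presuppose recording of treatment-related AEs, so that section 10 is inconsistent rather than clearly exclusionary. That is fair, but the inconsistency is a further reason to amend, because sites would have to choose between readings.

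Two supporting points carry less weight. The IST item can be read as a specific exception to the general laboratory rule, although the text does not say so. Secondary malignancy remains an AE unless it is attributed to IST.

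**Conclusion.** The concern holds and should be fixed. As written, serious events attributed to IST fall outside the AE and SAE definitions and have no stated route to the DSMC. This is a gap in classification and routing, not a total loss of data, and it does not mean there is no oversight.

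The number of events affected cannot be computed, since the documents give no infection, toxicity or attribution rates. The counts in the working describe the text and do not measure impact. No direction of bias in by-arm AE counts is established, and the primary endpoint, sample size and power statement are untouched. The conclusion rests on the protocol text alone; a provision in the institutional monitoring plan could supply a route that is not visible here.

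**What to change.** Amend sections 6.6, 10.1 and 10.5 with the same wording in each, so that the IST exclusion covers only non-serious events below CTCAE grade 3. State that the following are recorded and graded in both arms regardless of attribution to IST, over the existing window in section 10.8:

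- any event meeting a section 10.2 criterion, including death;
- grade 3 or higher infection or organ toxicity;
- relapse;
- secondary malignancy.

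Add to section 10.5 that these are included by arm in the existing DSMC report. Then reconcile the result with the AE definition and laboratory rule in section 10.1 and with the relatedness scale in section 10.7. The grade 3 threshold is a choice; it matches the endpoints in section 3.2.

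A narrower alternative is one sentence in section 10.5 adding serious IST-attributed events and the grade 3 or higher endpoints to the DSMC report. That would state the route but leave the definitions in conflict. It would also need a recording requirement for serious events that are neither AEs nor endpoints.

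The cost is one qualifier in three sections, the reconciling edits, and additional case report form and SAE entries in a 40-patient study. Their number cannot be computed, but relapse and grade 3 or higher infection and organ toxicity are already collected, and the grading scale, recording window and DSMC report already exist. Clinical management does not change.

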## 10.2 Serious Adverse Events

An adverse event should be classified as an SAE if it meets one of the following criteria:

Fatal	Adverse event results in death.
Life threatening:	The adverse events placed the subject at immediate risk of death. This classification did not apply to an adverse event that hypothetically might cause death if it were more severe.
Hospitalization:	It required or prolonged inpatient hospitalization. Hospitalizations for elective medical or surgical procedures or treatments planned before enrollment in the treatment plan or routine check-ups are not SAEs by this criterion. Admission to a palliative unit or hospice care facility is not considered to be a hospitalization.
Disabling/incapacitating	Resulted in a substantial and permanent disruption of the subject's ability to carry out normal life functions.
Congenital anomaly or birth defect:	An adverse outcome in a child or fetus of a subject exposed to the molecule or treatment plan regimen before conception or during pregnancy.
Medically significant:	The adverse event did not meet any of the above criteria, but could have jeopardized the subject and might have required medical or surgical intervention to prevent one of the outcomes listed above.

## 10.3 Disease-Related Events and/or Disease-Related Outcomes Not Qualifying as SAEs

An event which is part of the natural course of the disease under study (i.e., disease progression) does not need to be reported as an SAE. However, if the progression of the underlying disease is greater than that which would normally be expected for the subject, or if the investigator considers that there was a causal relationship between treatment with investigational product or protocol design/procedures and the disease progression, then this must be reported as an SAE.

#### 10.4 Unexpected Adverse Event

An unexpected adverse event is defined as an event that has a nature or severity, or frequency that is not consistent with the applicable investigator brochure, or the prior medical condition of the subject or other treatment given to the subject. "Unexpected," as used in this definition, refers to an adverse drug experience that has not been previously observed and reported in preclinical or clinical studies rather than an experience that has not been anticipated based on the pharmacological properties of the study drug.

#### 10.5 Monitoring and Recording Adverse Events

All AEs will be assessed by the investigator or qualified designee and recorded in the CRFs. The investigator should attempt to establish a diagnosis of the event on the basis of signs, symptoms and/or other clinical information. In such cases, the diagnosis should be documented as the adverse event and/or serious adverse event and not described as the individual signs or symptoms. The following information should be recorded:

- Description of the adverse event using concise medical terminology
- Description as to whether or not the adverse event is serious, noting all criteria that apply
- The start date (date of adverse event onset)
- The stop date (date of adverse event resolution)
- The severity (grade) of the adverse event
- A description of the potential relatedness of the adverse event to study drug, a study procedure, or other causality
- The action taken due to the adverse event
- The outcome of the adverse event

If an adverse event occurs as a result of study participation, the PI will ensure appropriate follow-up is carried out until the effects of the adverse event are resolved. If the study staff becomes aware of any unanticipated severe adverse reactions due to study participation, the circumstances will be immediately reported to the IRB. To note, clinical events related to IST will not be reported as adverse events, since both discontinuation or prolonged continuation of IST are used in practice. All AEs and SAEs will be reported to the DSMC at least annually.

#### 10.6 Grading Adverse Event Severity

All AEs will be graded in severity according to the NCI Common Terminology Criteria for Adverse Events (CTCAE) Version 4.0. If a CTCAE criterion does not exist, the investigator should use the grade or adjectives: Grade 1 (mild), Grade 2 (moderate), Grade 3 (severe), Grade 4 (life-threatening), or Grade 5 (fatal) to describe the maximum intensity of the adverse event.

## 10.7 Attribution of an Adverse Event

Association or relatedness to the study agent will be assessed by the investigator as follows:

- **Definite:** The event follows a reasonable temporal sequence from exposure to the investigational agent, has been previously described in association with the investigational agent, and cannot reasonably be attributed to other factors such as the subject's clinical state, other therapeutic interventions or concomitant medications; AND the event disappears or improves with withdrawal of the investigational agent and/or reappears on re-exposure (e.g., in the event of an infusion reaction).
- **Probable:** The event follows a reasonable temporal sequence from exposure to the investigational agent and has been previously been described in association with the investigational agent OR cannot reasonably be attributed to other factors such as the subject's clinical state, other therapeutic interventions or concomitant medications.
- **Possible:** The event follows a reasonable temporal sequence from exposure to the investigational agent, but could be attributable to other factors such as the subject's clinical state, other therapeutic interventions or concomitant medications.
- **Unlikely:** Toxicity is doubtfully related to the investigational agent(s). The event may be attributable to other factors such as the subject's clinical state, other therapeutic interventions or concomitant medications.
- **Unrelated:** The event is clearly related to other factors such as the subject's clinical state, other therapeutic interventions or concomitant medications.

For general AE assessment, an AE is considered related if it is assessed as definitely, probably, or possibly related; unrelated if it is assessed as unlikely related or unrelated.

## 10.8 Adverse Event Recording Period

AEs will be monitored and recorded in study-specific case report forms (CRFs) from the time of consent through the end of active follow-up (~12 months after randomization).

## 11. Data and Safety Monitoring Plan

Institutional support of trial monitoring will be in accordance with the FHCRC/University of Washington Cancer Consortium Institutional Data and Safety Monitoring Plan. Under the provisions of this plan, FHCRC Clinical Research Support (CRS) coordinates data and compliance monitoring conducted by consultants, contract research organizations, or FHCRC employees unaffiliated with the conduct of the study. Independent monitoring visits occur at specified intervals determined by the assessed risk level of the study and the findings of previous visits per the institutional DSMP.

In addition, protocols are reviewed at least annually and as needed by the Consortium Data and Safety Monitoring Committee (DSMC), FHCRC Scientific Review Committee (SRC) and the FHCRC/University of Washington Cancer Consortium Institutional Review Board (IRB). The review committees evaluate accrual, adverse events, stopping rules, and adherence to the applicable data and safety monitoring plan for studies actively enrolling or treating subjects. The IRB reviews the study progress and safety information to assess continued acceptability of the risk-benefit ratio for human subjects. Approval of committees as applicable is necessary to continue the study.

The trial will comply with the standard guidelines set forth by these regulatory committees and other institutional, state and federal guidelines.

